### **11.13 Maintaining and Breaking Study Blind**

Participating subjects, NIDA staff, the VA Protocol Chairperson, study personnel at each site, and individuals serving as adjudicators for inclusion criteria and study endpoints will be blinded to treatment assignment from the day of randomization (Study Day 8) forward. Subjects will be blinded to the change in study drug (from ACZM to lorcaserin or matched placebo) on Study Day 8, and appropriate caution will be exercised by site staff in conversations with subjects to maintain this blind.

Every study subject will be encouraged to carry a wallet card that identifies him or her as a subject in a clinical research study. The card will provide the emergency contact information for the SI, study physician and the study's research pharmacist. The card will also instruct the non-study physician rendering emergency care to provide information to the study site physician with regards to that care.

The study blind should not be broken except in a medical emergency, where knowledge of the study drug received is necessary for the medical management of the subject, or for a regulatory requirement. The SI should contact the CSPCRPCC Study Pharmacist and NIDA Medical Monitor to request an unblinding authorization.

If the blind is broken for an individual subject due to a medical emergency, the following information must be recorded in the subject's source documents: Date and time of unblinding together with the reason for the unblinding, and all associated AE information. The source documents should note that the subject's treatment assignment was unblinded and include the date of the unblinding to enable censoring of any data as appropriate.

Treatment assignment for all subjects within the study will remain blinded except as noted above and will not be revealed until all final clinical data have been entered into the database and all data queries have been resolved for all subjects, i.e., after the database is locked.

## **12 ASSESSMENT METHODS**

Clinical assessments will be conducted according to the **Schedule of Events** (Table 3) and are briefly described as follows:

### **12.1 Subject Locator Form**

A Subject Locator Form will be completed and will be kept securely at the clinical site, separate from the subject's study data. Data collected on the Subject Locator Form will be used to facilitate contact with the subject during the research and follow-up. Subjects will be asked to provide locator information including their residential street address and a working telephone number, and the contact information for a relative or friend who can reach the subject in emergencies.

### **12.2 Medical History**

During screening, a medical history will be collected and reviewed by a clinical staff member with medical training to determine subject eligibility before enrollment.

### **12.3 Smoking and Alcohol History**

The Smoking History Survey is a modified version of the Mayo Nicotine Dependence Center Patient Questionnaire (1991) and will be administered by a research assistant. The Smoking History Survey asks subjects the following: how many cigarettes per day they smoke and how many times they have attempted to quit (including methods). Information on other non-cigarette tobacco products is also noted. Subjects will also be asked about their alcohol consumption during the last 30 days: how many days did they have at least one drink; how many drinks did they usually have on the days they drank; and the largest number of drinks consumed on any one day during the 30-day period.

### **12.4 Psychiatric History**

Structured Clinical Interview for DSM-5 – Research Version (SCID-5-RV) will be conducted by appropriately trained clinical staff. The SCID-5-RV will evaluate the subject's history or current diagnosis of the following categories of neuropsychiatric disorders: psychosis, bipolar illness, major depression, anorexia nervosa or bulimia, or presence of current anxiety disorder.

### **12.5 Demographics**

Age, gender, race, ethnicity, years of education, usual employment pattern in the last 30 days, and marital status data will be collected on all consented subjects, whether or not they are randomized.

### **12.6 Addiction Severity Index-Lite (ASI-Lite)**

The ASI-Lite is a multidimensional, semi-structured, clinician-administered interview. It is widely used in the substance abuse field and has good reliability and validity. It is designed to provide a comprehensive assessment of functioning in seven areas – medical, employment, alcohol use, drug use, legal, family/social relationships, and psychiatric symptoms. For each of the seven functional areas, the instrument produces composite scores, which are based on the respondent's answers to particular items.

### **12.7 Physical Exam**

A physical exam of the head, eyes, ears, nose and throat, cardiovascular system, lungs, abdomen (liver/spleen), extremities, skin, brief neurological exam, musculoskeletal system and general appearance will be performed by a licensed study staff member with medical training. Subject's height will also be recorded on this form.

### **12.8 Vital Signs and Weight**

Vital signs to be assessed include temperature, blood pressure (sitting after 3 minutes), pulse rate, and respiratory rate. Weight (in pounds) will also be measured. Body Mass Index (BMI) will be calculated at screening to verify inclusion criteria #8.

### **12.9 Pregnancy Test**

An FDA-approved urine pregnancy test designed to measure  $\beta$ -human chorionic gonadotropin will be used. All female subjects will be tested regardless of their child-bearing capacity.

### **12.10 12-lead ECG**

A 12-lead ECG will be performed on all subjects according to standard procedures. A licensed physician or a non-physician who is certified/accredited by the participating institution to read ECGs must read all ECGs. A board-certified cardiologist can be consulted, if needed.

### **12.11 Beck Depression Inventory-Second Edition (BDI-II)**

The Beck Depression Inventory Second Edition (BDI-II) is a 21-item self-report instrument intended to assess the existence and severity of symptoms of depression. This assessment includes items intending to index symptoms of severe depression, which would require hospitalization. When presented with the BDI-II, the subject will be asked to consider each statement as it relates to the way they have felt for the past two weeks. Subsequent assessments of BDI-II during treatment will be compared to the subject's previous assessment in order to evaluate change (i.e. worsening.)

The subject will be asked to consider each statement as it relates to the way he/she has felt during the assessment period as described above. Each of the 21 items corresponding to a symptom of depression is summed to give a single score for the BDI-II. There is a four-point scale for each item ranging from 0 to 3. A total score of 0-13 is considered minimal depression range, 14-19 is mild, 20-28 is moderate, and 29-63 is severe.

During the treatment phase, the following action will be taken by the site investigator/team in response to BDI-II score:

- Score < 20: no action
- Score 20-28: consider further evaluation of possible clinical depression
- Score > 28: discontinue study drug and refer to mental health practitioner or to primary care physician for evaluation of clinical depression

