## **11 STUDY PROCEDURES**

**Table 3, Schedule of Events, provides a detailed time table of study activities.**

**Table 3. Schedule of Events**

Study Phase	Screen	Treatment Phase a													Early Term	Follow-Up	
Study Week	-3 to -1 a	1 (Study Day 1) b	2 (Study Day 8)	3	4	5	6	7	8	9	10	11	12	13		14	16
Informed Consent	X																
Enrollment		X															
Randomization			X														
Demographics	X																
Medical History	X																
DSM-5 / (SCID-5-RV)	X																
Physical Exam	X														X		X
Vital Signs/Weight	X	X	X	X	X	X	X	X	X	X	X	X	X	X	X	X	X
12-lead ECG	X							X							X		X
C-SSRS (initial & since last visit)	X	X	X	X	X	X	X	X	X	X	X	X	X	X	X	X	X
BDI - II	X		X		X		X		X		X		X		X	X	
Prior/Concomitant Medications	X	X	X	X	X	X	X	X	X	X	X	X	X	X	X	X	X
Brief Subs. Craving Scale (BSCS)		X	X	X	X	X	X	X	X	X	X	X	X	X	X		
Drug Dispensing/Reconciliation		X h	X	X	X	X	X	X	X	X	X	X	X	X	X	X	
Adverse Events	X	X h	X	X	X	X	X	X	X	X	X	X	X	X	X	X	X
Blood/Plasma																	
Plasma (lorcaserin)				X				X									
Plasma (acetazolamide)			X														
Blood Chemistries c	X							X							X		X
Hematology d	X							X							X		X
Urine																	
Urine Pregnancy Test	X	X*	X	X	X	X	X	X	X	X	X	X	X	X	X	X	X
Medical Urinalysis e	X							X							X		X
Urine Toxicology Screen f	X i																
Urine Fentanyl	X i																
Urine Cotinine	X i	X	X	X	X	X	X	X	X	X	X	X	X	X	X	X	X
Urine BE		X	X	X	X	X	X	X	X	X	X	X	X	X	X	X	X
Urine Alcohol Test (EtG)	X i	X	X	X	X	X	X	X	X	X	X	X	X	X	X	X	X
Substance Use																	
Smoking & Alcohol History	X																
ASI –Lite		X												X	X		

Study Phase	Screen	Treatment Phase a													Early Term	Follow-Up		
Study Week	-3 to -1 a	1 (Study Day 1) b	2 (Study Day 8)	3	4	5	6	7	8	9	10	11	12	13		14	16	
SUR (initial & since last visit)	X	X h	X	X	X	X	X	X	X	X	X	X	X	X	X	X	X	X
AiView Data Collection (device)				X	X	X	X	X	X	X	X	X	X	X	X	X		
Behavioral Therapy																		
CBT (cocaine)		X	X	X	X	X	X	X	X	X	X	X	X	X	X			
Quit to Quit (alcohol intervention)		X	X g	X g					X g									

\* Procedure that will be completed just prior to enrollment.

a Screening may take place during one or multiple visits within 21 days of providing Informed Consent.

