### **11.9 Situations Requiring Study Drug Discontinuation**

**A subject should no longer receive study drug if:**

- The subject wishes to stop taking study drug or no longer wishes to participate in the study.
- The subject develops a medical illness, complication or side effects from study drug, and/or has an adverse experience which, in the opinion of the SI or physician, precludes safe continuation of the study drug.
- The subject fails to take study drug (for any reason) for 14 consecutive days.
- The female subject becomes pregnant (as evidenced by a positive pregnancy test) at any time during study.
- The subject has a BDI-II score of > 28 or scores > 0 on question # 9 (suicidal thoughts and wishes) will be referred to a mental health practitioner or primary care physician for further evaluation and follow-up.
- The subject has clinically significant abnormal laboratory findings and vital signs (after confirmatory repeat measurements) as deemed by the SI or physician, including but not limited to;
  - o CrCl < 30 ml/min
  - o LFT > 5 times UNL
  - o Uncontrolled hypertension; SBP  $\geq$  180 mmHg and/or DBP  $\geq$  110 mmHg

If a subject loses substantial weight during the treatment period and, in the opinion of the site physician, he/she is approaching the lower limit of acceptable weight, the subject will be counselled for appropriate eating and nutrient intake, and the subject's weight will be followed closely during each subsequent visit. If the subject continues to lose weight so that, in the opinion of the site physician, it is unsafe to continue treatment, study medication will be discontinued.

If a subject expresses suicidal thoughts or exhibits acute psychosis or suicidal/homicidal behavior, the subject will be referred to a local treatment center, emergency department or be hospitalized as appropriate and study drug will be discontinued.

Subjects who are no longer receiving study drug will continue to be followed and will complete regularly scheduled assessments to provide as much data as possible. These subjects will be paid for each clinic visit but will not be rewarded for any additional bonus payments (including device-related rewards).

NOTE: Subjects who become pregnant during study participation will be immediately discontinued from the study drug. Subjects will be asked to sign a release of information form for study personnel to access medical records and information regarding the outcome of the pregnancy.

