### **12.12 Columbia Suicide Severity Rating Scale (C-SSRS)**

The C-SSRS is a 2-page form asking questions about suicidal ideation, intensity of ideation, and suicidal behavior developed by Posner and collaborators at the New York State Psychiatric Institute (Oquendo *et al.*, 2003). The "baseline/screening" version of the C-SSRS will be used to assess lifetime suicidality. The "since last visit" C-SSRS will be used to assess current suicidality. This scale is intended for use by trained administrators. The questions contained in the C-SSRS are suggested probes. Ultimately, the determination of the presence of suicidality depends on clinical judgment. Training is required before administering the C-SSRS through a 30-minute interactive slide presentation followed by a question-answer session through the Columbia University Medical Center. Those completing the training are certified to administer the C-SSRS, and must provide a valid training certificate for the study's regulatory files.

NOTE: If a subject expresses suicidal thoughts or exhibits acute psychosis or suicidal/homicidal behavior, the subject will be referred to a local treatment center, emergency department or be hospitalized as appropriate and study drug will be discontinued.

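### Section 12.11 tells sites to do nothing for a BDI-II total below 20, with no exception for item 9, while Section 11.9 lists any item 9 score above 0 as a reason to stop study drug

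*Combined protocol and SAP*

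**What the plan says.** Section 12.11 defines the BDI-II score as the sum of 21 items, each scored 0 to 3, and then lists what the site team will do in response to that score during treatment. The lowest band is "Score < 20: no action". In the middle band, 20 to 28, the team is asked only to think about assessing the subject for depression. The top band is "Score > 28: discontinue study drug and refer to mental health practitioner or to primary care physician for evaluation of clinical depression".

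There is no line for item 9 and no cross-reference to Section 11.9.

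Section 11.9 opens its list with "A subject should no longer receive study drug if" and includes this bullet: "The subject has a BDI-II score of > 28 or scores > 0 on question # 9 (suicidal thoughts and wishes) will be referred". The referral is to a mental health or primary care clinician. No total score is attached to the item 9 trigger.

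Later in the same section a separate rule says: "If a subject expresses suicidal thoughts or exhibits acute psychosis or suicidal/homicidal behavior, the subject will be referred to a local treatment center". That rule also provides for emergency or inpatient care and stops study drug. The note in Section 12.12 repeats the rule, ending "hospitalized as appropriate and study drug will be discontinued".

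**The concern.** The two sections give site staff different instructions for the same completed form. Section 12.11 is where staff would look when they score the BDI-II. It carries over the first trigger in the 11.9 bullet (total above 28) as stop and refer, and it leaves out the second (item 9 above 0). A site that follows 12.11 as written would take no step for a subject who endorses suicidal thoughts on the form but whose total is low.

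This is a suicidality rule in a trial of a drug for which Section 3.4.7.1 reports discontinuation for depression in 0.9% of treated patients against 0.5% on placebo. With 10 or more sites, the response should not depend on which section a site opens.

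**Working it through.** The plan gives no figure to reproduce here. The check sets the two rules side by side and asks whether one subject can fall under both.

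**Can the rules collide?** Item 9 scores 0 to 3 and the total runs from 0 to 63. With item 9 = 1 and every other item 0, the total is 1. Adding points on other items gives any total up to 19. So item 9 above 0 is compatible with every total from 1 to 19.

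| BDI-II total, with item 9 above 0 | Section 12.11 | Section 11.9 |
|---|---|---|
| 1 to 19 | Nothing | On the stop-drug list; refer |
| 20 to 28 | Consider evaluating for depression | On the stop-drug list; refer |
| Above 28 | Stop and refer | On the stop-drug list; refer |

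The sections agree only in the last row.

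**What does 11.9 require for item 9?** The bullet is ungrammatical. Its heading says stop and its verb says refer. Three things favour stop plus refer:

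1. The bullet sits under a heading about ending study drug.
2. Section 12.11 renders the other trigger in the same bullet as stop plus refer.
3. The expressed-suicidal-thoughts rule in 11.9 and 12.12 also stops drug.

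If the bullet means referral only, it still contradicts doing nothing.

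**Can such subjects be in the trial?** Yes. Section 8.3 excludes a screening BDI-II total of 20 or more, so everyone eligible by that criterion screens in the lowest 12.11 band. No eligibility criterion names item 9. The C-SSRS ideation exclusion covers only Questions 4 and 5.

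**How many forms does the rule govern?** These are ceilings that assume no dropout. They count forms scheduled, not conflicts.

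- Treatment-phase BDI-II visits in Table 3: Weeks 2, 4, 6, 8, 10 and 12, which is 6. Week 2 is the randomisation visit, so 5 follow dosing on randomised drug. Screening, Early Termination and Week 14 are not counted.
- Randomised, from 272 enrolled and the 5% early loss assumed in Section 14.1: 272 × 0.95 = 258.4, about 258.
- Scheduled forms: 258 × 6 = 1,548.
- After randomised dosing: 258 × 5 = 1,290.

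**The case against.** The strongest reply is that 12.11 is a depression-severity ladder and was never meant as the suicidality rule. Its upper bands are about evaluating clinical depression. Other parts of Section 12 (vital signs, pregnancy test, blood chemistries) also leave their stopping rules to 11.9, so 11.9 could be said to govern throughout. The limit of this argument is that those sections are silent, whereas 12.11 affirmatively tells staff to do nothing.

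A second reply is that the gap is largely covered. The C-SSRS is given at every visit by trained staff, and the expressed-suicidal-thoughts rule has no score threshold. Endorsing item 9 in writing could naturally count as expressing such thoughts. These safeguards are substantial. A miss needs a subject who endorses item 9 on a self-report form and reports nothing on the C-SSRS, at a site that acts on 12.11 alone. But the protocol does not say that a written item 9 answer counts as expressing suicidal thoughts. If it does, 12.11 conflicts with that rule as well.

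Two further points stand. That 11.9 requires a stop for item 9 is partly inferred from a garbled sentence; the firm contradiction is between doing nothing and referring. And the form counts show only how often the rule is applied, not how often it fails.

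**Conclusion.** The inconsistency is real. For any subject with item 9 above 0 and a total of 1 to 19, 12.11 and 11.9 give incompatible instructions on either reading of 11.9. They also differ for totals of 20 to 28. Stop plus refer is the better-supported intention, but the sponsor needs to confirm it.

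The number of subjects affected cannot be estimated, because the documents give no item 9 endorsement rate. The correction should be made because following 12.11 as written gives the wrong response to a suicidality signal. The overlapping safeguards limit the practical risk, and no effect on the primary outcome is claimed.

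**What to change.** Add a line to the 12.11 list along these lines: *Item 9 above 0, whatever the total: apply Section 11.9 (stop study drug and refer).*

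Reword the 11.9 bullet so that it states both the trigger and the action: *BDI-II total above 28, or item 9 above 0: study drug is stopped and the subject is referred to a mental health practitioner or primary care physician.* This agrees with the expressed-suicidal-thoughts rule in 11.9 and 12.12.

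If the sponsor's clinicians intend referral only for item 9, take that trigger out of the stop-drug list and say so in both sections. They should settle this with the Week 2 form in mind: it falls on the randomisation day, and subjects who endorse item 9 are not excluded at entry by that answer alone.

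The cost is one added line, one reworded bullet and a reminder to sites. No new assessment is needed.

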### **12.12 Columbia Suicide Severity Rating Scale (C-SSRS)**

The C-SSRS is a 2-page form asking questions about suicidal ideation, intensity of ideation, and suicidal behavior developed by Posner and collaborators at the New York State Psychiatric Institute (Oquendo *et al.*, 2003). The "baseline/screening" version of the C-SSRS will be used to assess lifetime suicidality. The "since last visit" C-SSRS will be used to assess current suicidality. This scale is intended for use by trained administrators. The questions contained in the C-SSRS are suggested probes. Ultimately, the determination of the presence of suicidality depends on clinical judgment. Training is required before administering the C-SSRS through a 30-minute interactive slide presentation followed by a question-answer session through the Columbia University Medical Center. Those completing the training are certified to administer the C-SSRS, and must provide a valid training certificate for the study's regulatory files.

NOTE: If a subject expresses suicidal thoughts or exhibits acute psychosis or suicidal/homicidal behavior, the subject will be referred to a local treatment center, emergency department or be hospitalized as appropriate and study drug will be discontinued.

### **12.13 Blood Chemistries**

Blood will be collected by the sites in serum separation evacuated venous blood collection tubes (e.g., Vacutainer®) and will be separated according to standard procedures and sent to a central clinical laboratory for testing (Q Solutions, Valencia, CA). Quantitative analysis will be performed for the following analytes: sodium, potassium, chloride, carbon dioxide, glucose, creatinine, calcium, alanine aminotransferase (ALT/SGPT), aspartate aminotransferase (AST/SGOT), gamma-glutamyltranspeptidase (GGT), total bilirubin, alkaline phosphatase (ALP), and blood urea nitrogen (BUN). Results will be made available to the clinical site staff upon completion of testing.

### **12.14 Hematology**

Blood will be collected by the sites in evacuated venous blood collection tubes containing anticoagulant (e.g., Vacutainer®) for hematologic assessments and sent to a central clinical laboratory for testing (Q Solutions, Valencia, CA). Complete blood counts (CBC) with differentials and platelet count will be performed. Quantitative analyses for hemoglobin, hematocrit, red blood cells, platelets, total white blood cells, neutrophils, lymphocytes, monocytes, eosinophils, and basophils will be performed. Results will be made available to the clinical site staff upon completion of testing.

### **12.15 Urinalysis**

Urine will be collected using the collection kit provided by the central clinical laboratory (Q Solutions, Valencia, CA) and analyzed for: specific gravity, pH, blood, protein, glucose, ketones, leukocytes, and nitrite. Results will be made available to the clinical site staff upon completion of testing.

### **12.16 Urine Drug Screen**

Urine samples will be tested for cocaine and other drugs of abuse (as noted in **Table 3, Schedule of Events**) using a multi-panel on-site test device (Branan ToxCup® DT14) to identify individuals potentially using illicit drugs.

### **12.17 Urine Fentanyl**

Urine samples will be collected and tested using an on-site one-step rapid fentanyl test stick to determine qualitative detection of fentanyl metabolite at 50 ng/mL cut-off concentration.

